- 1) Clinical outcomes differences between PCI treatment vs optimal medical treatment in patients with at least one FFR positive lesion (group c vs group d)
- 2) Staged PCI versus acute (during PPCI) revascularisation of FFR positive lesions (group a vs group c)
- 3) Optimal Medical Treatment versus PCI treatment of FFR negative lesions (group b + f vs group e)

In order to balance the number of patients in these subgroups we chose for a 1:2 randomisation pattern.

[figure not shown]

Figure 2: Subgroups resulting from this randomisation.

Endpoints

Primary endpoint:

Composite endpoint of all cause mortality non-fatal Myocardial Infarction, any Revascularisation and Cerebrovascular Events (MACCE) at 12 months between groups (a+b versus c-f).

Secondary endpoints:

1. Primary endpoint at 24 and 36 months as well as outcomes of each component of the primary endpoint at 12, 24 and 36 months.
2. Primary endpoint rates at 12, 24 and 36 months in the subgroup of patients receiving staged or acute PCI treatment for FFR positive lesions in the non-IRA vs the subgroup of patients with FFR positive lesion that received optimal medical treatment. {figure 2, subgroups (a+c) vs subgroup d}
3. Primary endpoint rates at 12, 24 and 36 months in the subgroup of patients receiving acute PCI treatment for FFR positive lesions in the non-IRA vs the subgroup of patients receiving staged PCI treatment for FFR positive lesions in the non-IRA (figure 2 subgroups a vs c)
4. Primary endpoint rates at 12, 24 and 36 months in the subgroup of patients receiving staged PCI treatment for FFR negative lesions in the non-IRA vs the subgroup of patients not receiving PCI treatment for FFR negative lesions in the non-IRA. (figure 2 subgroups e vs b+ f)
5. Composite endpoint of Cardiac death, Myocardial Infarction, any Revascularisation, Stroke and Major bleeding at 12, 24 and 36 months (NACE i.e. Net Adverse Clinical Events)
6. A composite of hospitalisation for heart failure and unstable angina pectoris at 12, 24, and 36 months
7. All cause mortality or Myocardial infarction at 12, 24 and 36 months

8. Any revascularisation at 12, 24 and 36 months
9. Stent thrombosis at 12 months, 24 and 36 months
10. Bleeding at 48 hr and 12 months.
11. Treatment costs 12 months, 24 and 36 months

Definitions

Death

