In the guideline guided group the staged non-IRA revascularisations can take place until day 45 post primary PCI. These will be called **staged non-IRA revascularisations** and will not be counted as an event revascularisation, unless the Clinical Event Committee considers these revascularisations as clinically not justifiable.

All urgent revascularisations (in both strategy arms) will be counted as events. All other revascularisations that do not qualify as **delayed** or **staged non-IRA revascularisations** will be counted as events. All revascularisations that will take place beyond the 45 days will also be counted as event revascularisations.

Clinically indicated:

A revascularization is clinically indicated if angiography shows a percent diameter stenosis $\geq 50\%$ (QCA) **and** if one of the following occurs:

- 1) A positive history of recurrent angina pectoris presumably related to the target vessel.
- 2) Objective signs of ischemia at rest (ECG changes) or during exercise test (or equivalent) presumably related to the target vessel.
- 3) Abnormal results of any invasive functional diagnostic test (e.g. Doppler flow velocity reserve, fractional flow reserve). The results of the test must be documented in the Case Report Form.

Not Clinically indicated are re-interventions for:

1. all stenoses in absence of ischemic signs or symptoms.

Stent Thrombosis

We follow the ARC definitions³⁰. Stent Thrombosis should be reported as a cumulative value at the different time points and with the different separate time points. Time 0 is defined as the time point after the guiding catheter has been removed and the patient left the Cathlab.

Timing

Acute stent thrombosis(*):	0 – 24 hours post stent implantation
Subacute stent thrombosis(*):	>24 hours – 30 days post stent implantation
Late stent thrombosis:	>30 days – 1 year post stent implantation
Very late stent thrombosis:	>1 year post stent implantation

(*) acute/subacute can also be replaced by early stent thrombosis. Early stent thrombosis (0 – 30 days) – this definition is currently used in the community.

We recognize three categories of evidence in defining stent thrombosis:

- 1) Definite
- 2) Probable
- 3) Possible

1) Definite* stent thrombosis

Angiographic confirmation of stent thrombosis†

The presence of a thrombus that originates in the stent or in the segment 5 mm proximal or distal to the stent and presence of at least 1 of the following criteria within a 48-hour time window:

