if at the time of hospital discharge he or she had a moderate deficit (substantial limitation of activity and capabilities) or a severe deficit (inability to live independently or work). Modified Rankin scale grade of > 4 (see below)

Modified Rankin Scale - Stroke severity assessment scale

Scale 0

No symptoms at all

Scale 1

No significant disability despite symptoms: able to carry out all usual duties and activities

Scale 2

Slight disability: unable to carry out all previous activities but able to look after own affairs without assistance

Scale 3

Moderate disability: requiring some help, but able to walk without assistance

Scale 4

Moderately severe disability: unable to walk without assistance, and unable to attend to own bodily needs without assistance

Scale 5

Severe disability: bedridden incontinent and requiring constant nursing care and attention

Urgent Revascularisation

Any PCI or bypass surgery for recurrent ischemia that in the investigators opinion can not be delayed for more than 24 hours and is defined by the investigator as a non-elective procedure.

Target Lesion revascularisation

TLR is defined as any ischemia-driven repeat PCI of the target lesion or bypass surgery of the target vessel. Target lesion is defined as the vessel segment composed by the treated segment including the adjacent 5mm distal and proximal to the treated segment.

Target Vessel revascularisation

TVR as any ischemia-driven repeat PCI or bypass surgery in any lesion of the target vessel. The target vessel is one of the 3 main epicardial coronary artery or bypass graft that contains the target lesion.

NYHA Classification of Heart Failure

Class I

No limitation of activities; patients suffer no symptoms from ordinary activities.

Class II

Slight, mild limitation of activity; patients are comfortable with rest or with mild exertion.

Class III

Marked limitation of activity; patients are comfortable only at rest.

Class IV

Patients who should be at complete rest, confined to bed or chair; any physical activity brings on

Killip Classification of Heart Failure

Class I

The absence of rales over the lung fields and the absence of an S3.

Class II

The presence of rales, that do not clear with coughing, over one half or less of the lung fields or the presence of an S3.

Class III

The presence of rales that do not clear with coughing, over more than half the lung fields.

Class IV

Cardiogenic shock

Cardiogenic Shock

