A total sample size of 858 patients (286 in the FFR-guided group, 572 in the control group) is sufficient to obtain a power of at least 80% with a two-sided false positive error rate (alpha) of 5% for rejecting the null-hypothesis of no difference when the endpoint incidence is 8% in the FFR guided group vs 14.5% in the control group, using the Pearson Chi-square test for two proportions assuming an asymptotic normal distribution with a normal approximation method.

Considering a 3% loss in follow-up a total of 885 (295/590) patients will be randomised in this trial. Categorical variables will be assessed with the use of χ^2 or Fisher's exact tests, whereas continuous variables will be assessed with the Wilcoxon rank-sum test.

The results in both groups for the primary endpoint as well as for the secondary endpoints will be presented as time to event curves (Kaplan-Meyer).

Trial Conduct

Cathlab procedure

The primary PCI will be performed within 12 hr after onset of symptoms, however patients with symptoms for more than 12 hr and ongoing ischemia can also be randomised.

Standard care cathlab techniques and equipment will be used to perform the coronary angiography imaging and primary PCI. Artery puncture site is left at the discretion of the operator, although radial approach is strongly recommended to avoid bleeding complications at the puncture site. A diagram or description of the coronary artery tree will be completed at the end of the procedure to indicate which segments have lesions with approximately 50% or more diameter stenosis. If the lesion extends over more than one segment the most proximal segment should be stated.

Assessment of left ventricle function or wall motion abnormalities are at the discretion of local practice.

Thrombosuction and pre-dilation of the lesion are left at the discretion of operator.

Intracoronary injection of nitrates followed by two orthogonal projections for culprit lesion evaluation and stent size choice are strongly recommended.

Stenting should by protocol be performed. Everolimus Eluting Xience V/ Prime /Expedition should be used in this study as these are at the moment the most safe drug-eluting stents clinically proven in this setting.

Post-dilation will be left at the discretion of the operator.

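### Whether an early, justified control-arm non-IRA PCI counts as a primary event depends on an urgency label set by the investigator, with no documented criterion and no stated masked override

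*Combined protocol and SAP*

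**What the plan says.** The primary endpoint (Endpoints) is a composite that includes "any Revascularisation and Cerebrovascular Events (MACCE) at 12 months between groups". Which revascularisations count is set out under Definitions, Revascularisation:

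- **Control arm.** "In the guideline guided group the staged non-IRA revascularisations can take place until day 45 post primary PCI". These are exempt unless the Clinical Event Committee finds them clinically unjustified.
- **FFR arm.** The only exemption is for a delayed non-IRA procedure that was specified at the end of the primary PCI and done in the same hospitalisation. Every other reintervention is an event.
- **Override.** "All urgent revascularisations (in both strategy arms) will be counted as events".

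Definitions, Urgent Revascularisation, supplies the deciding term: "Any PCI or bypass surgery for recurrent ischemia that in the investigators opinion can not be delayed for more than 24 hours". The investigator must also define the procedure as non-elective.

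On masking, the Trial design description hides the FFR values from the treating cardiologist, who must not be the operator. It describes no masking to allocation.

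On adjudication, the List of Abbreviations describes endpoints as centrally adjudicated. The Summary and Trial management give event adjudication to an independent committee. The specific task given to that committee for revascularisations (Trial design description) is to classify them as clinically indicated or not.

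**The concern.** For a control-arm non-IRA PCI that falls within 45 days and is clinically justified, urgency is the one remaining question that decides between exempt and event. Two of its three conditions are the investigator's own view: that the procedure cannot wait beyond 24 hours, and that it is non-elective. The third, recurrent ischaemia, is a clinical condition but is left undefined. No ECG, biomarker, admission or other recorded fact is asked for.

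The rule is worded for both arms but acts mainly on one. In the FFR arm the label can change the status only of a delayed in-hospital procedure. In the control arm it can change the status of any staged PCI in a 45-day window.

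A judgement made with knowledge of the arm can therefore move the primary endpoint in one arm. If procedures that could have waited are called urgent, control events are added and the comparison tilts towards the FFR strategy. If urgent procedures are recorded as staged, control events are lost and power falls.

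**Working it through.** **1. The plan's own figure.** Statistical Considerations asks for "a power of at least 80% with a two-sided false positive error rate (alpha) of 5" per cent, "when the endpoint incidence is 8% in the FFR guided group vs 14.5% in the control group", and gives "A total sample size of 858 patients (286 in the FFR-guided group, 572 in the control group").

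With pooled variance, 1:2 allocation and no continuity correction:

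- n(FFR) = [1.96·√(p̄(1−p̄)·1.5) + 0.8416·√(p₁(1−p₁) + p₂(1−p₂)/2)]² / (p₂−p₁)²
- p̄ = (0.08 + 2×0.145)/3 = 0.1233
- n(FFR) = (0.7893 + 0.3099)² / 0.065² = 286, so 286 + 572 = 858, with power 0.800
- 858/0.97 = 884.5, rounded up to 885, which agrees with "Considering a 3% loss in follow-up a total of 885 (295/590) patients will be randomised in this trial"

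The sample size reproduces and is not in dispute.

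**2. The largest pool open to the label.** Statistical Considerations assumes that half of controls are FFR positive with 70% revascularised, and half FFR negative with 50% revascularised (the complement of the 50% not revascularised).

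- 0.5×0.70 + 0.5×0.50 = 0.60
- 0.60×572 = 343 evaluable controls, or 0.60×590 = 354 randomised controls

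**3. Adding control events.** Let f be the share of staged PCIs called urgent although they could have waited. The documents give no value for f, so it is an assumption, shown from 1% to 10%. A patient who has another primary event adds nothing to the composite. Assuming relabelling is independent of other events, the added control rate is 0.60 × f × (1 − base rate).

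I took no true difference, with both arms at 8% or both at 14.5%, and used the plan's pooled test at 286/572. Worked case, f = 5% and base rate 8%:

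- added rate = 0.60×0.05×0.92 = 0.0276, so the control rate is 0.1076
- pooled rate = (286×0.08 + 572×0.1076)/858 = 0.0984
- null standard error = √[0.0984×0.9016×(1/286 + 1/572)] = 0.02157
- actual standard error = √[0.08×0.92/286 + 0.1076×0.8924/572] = 0.02062
- P(significant, favouring FFR) = Φ[(0.0276 − 1.96×0.02157)/0.02062] = Φ(−0.71) = 0.24

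In each range below, the lower value is for a base rate of 14.5% and the upper for 8%.

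| f | Points added | Patients added (of 572) | Two-sided rejection (nominal 5%) | Favouring FFR (nominal 2.5%) |
|---|---|---|---|---|
| 1% | 0.51–0.55 | about 3 | 5.3–5.6% | 3.8–4.4% |
| 2% | 1.03–1.10 | about 6 | 6.6–7.9% | 5.7–7.4% |
| 5% | 2.56–2.76 | 15–16 | 15–24% | 15–24% |
| 10% | 5.13–5.52 | 29–32 | 45–67% | 45–67% |

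At f = 5% the shift is 2.56/6.5 = 39% to 2.76/6.5 = 42% of the planned 6.5-point difference.

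**4. A smaller pool.** Statistical Considerations expects 60% of controls to have an exercise test, 20% a nuclear scan and 20% no test. Suppose only the untested fifth is exposed and is staged at the same rate (an assumption). The pool is 0.20×354 = 71, or 12% of controls. Then f = 5% gives 0.12×0.05 = 0.006, the same product as 0.60×0.01. That is the first row of the table: 5.3–5.6%, close to nominal.

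**5. Losing control events.** Keep the FFR arm at 8% and suppose urgent control procedures are recorded as staged. Control rates of 13.5%, 12.5% and 11.5% (1, 2 and 3 points lost) give power of 67%, 51% and 35%.

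**The case against.** **Central adjudication.** The plan sends endpoint events to an independent committee, and a revascularisation counted because it is urgent is such an event. A reader might infer that the site's label is final, but the documents do not say that. They also do not say that the committee may set the label aside, and a committee applying the definition as written would be confirming what the investigator's opinion was. Nor is it said to be masked to arm. The gap stands in that form.

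**A clinical condition exists.** Without recurrent ischaemia a staged PCI cannot meet the definition, whatever the view of its timing. That is right. What is missing is a documented or objective criterion, not every criterion.

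**The exposed pool is smaller.** A PCI booked after a stress test is an unlikely candidate for the urgent label. This also stands: 60% of controls is a ceiling, and with a small pool the effect is near nominal.

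**Direction.** A reader might infer that the rule must favour the FFR strategy. The documents do not support that, since misclassification can also remove control events. A reader might also infer that the operator who saw the FFR values makes the urgency call. The definition says only *investigator*, and the staged-PCI decision belongs to a treating cardiologist who is blinded to FFR values.

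**A strict definition is not free.** Requiring rest angina plus ECG change or biomarker rise would change the endpoint. Ischaemic symptoms with a biomarker rise and fall already meet the spontaneous MI definition. An urgent PCI for rest angina with neither finding would become exempt in controls only. I accept this, and the fix avoids it.

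**Conclusion.** The concern holds as a weakness in a stated endpoint rule. For a justified control-arm non-IRA PCI up to day 45, event status depends on an investigator's opinion. There is no documented criterion, no described masking to allocation, and no stated power for a masked committee to overrule it. The one-sided reach follows from the 45-day exemption existing only in the control arm. That the investigator knows the arm is inferred: the masking described covers FFR values only, and the two strategies differ visibly.

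The size is uncertain. It rests on an unsourced relabelling share, a pool of at most 60% of controls, and independence from other events. At 1–2% relabelling of the full pool the two-sided error is 5.3–7.9%; at 5–10% it is 15–67%. These are sensitivity figures, and a reader should not take the upper ones as a forecast. In the other direction, power could fall to between 67% and 35% for 1 to 3 points lost. The plan should be changed because the remedy is cheap, but nothing here shows that bias has to occur.

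**What to change.** 1. Amend the Revascularisation and Urgent Revascularisation definitions so that, for endpoint purposes, the existing clinical event committee decides urgency from source documents with allocation and FFR values removed. Record the investigator's label, but do not make it decisive. Clinical care is unaffected.
2. Have the committee pre-specify in its charter which documented facts it will weigh. Do not impose a new mandatory ECG or biomarker threshold, which would change the endpoint.
3. Pre-specify a sensitivity analysis of the primary endpoint that counts none, then all, of the non-IRA revascularisations performed after the index procedure and within 45 days, in both arms. The first version removes the label's influence, at the price of dropping genuine early urgent procedures. The second is only an outer bound, because it would turn the roughly 60% of controls expected to have staged PCI into events.

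The cost is an amendment to two definitions and the charter, redaction of the committee's packets, and a little more committee and analysis work. The committee already classifies every revascularisation.

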Must fulfil one of the following criteria:

1. Systolic blood pressure < 90 mmHg for at least 30 minutes

OR

The need for supportive measures to maintain a systolic blood pressure > 90 mmHg

AND

End-organ hypo-perfusion (cool extremities or urine output < 30 ml/h and a heart beat > 60 bpm)

OR

2. Cardiac Index < 2.2 l/min per square meter body surface area

AND

a pulmonary capillary wedge pressure of at least 15 mmHg

AND

End-organ hypo-perfusion (cool extremities or urine output < 30 ml/h and a heart beat > 60 bpm)

Major bleeding definitions

Multiple clinical and laboratory definitions of bleeding will be used for full assessment of the risk of bleeding. These definitions will be based on criteria from the Global Utilization of Streptokinase

and Tissue Plasminogen Activator for Occluded Coronary Arteries (GUSTO) trial³¹ (mild, moderate, or severe or life-threatening bleeding on the basis of use or non use of transfusions and the presence or absence of hemodynamic compromise), the Thrombolysis in Myocardial Infarction (TIMI) trial³² (minor or major bleeding on the basis of clinical and laboratory findings), and the Acute Catheterization and Urgent Intervention Triage Strategy trial (ACUITY; NCT00093158)³³ (major bleeding on the basis of detailed clinical assessment, changes in the hemoglobin level, hematomas >5 cm, and the need for blood transfusion).

For the bleeding secondary endpoint the TIMI (major and minor) criteria will be used,

However for further descriptive value the criteria for Acuity and GUSTO will also be captured in the database.

Detailed description of bleeding following different trials

GUSTO

Severe or Life Threatening

Either intracranial haemorrhage or bleeding that causes hemodynamic compromise and requires intervention

Moderate

Bleeding that requires blood transfusion but does not result in hemodynamic compromise

Mild

Bleeding that does not meet the criteria for severe or moderate

TIMI

Types of TIMI Bleeding

1. Major

Any intracranial bleeding

OR

Clinically overt signs of hemorrhage associated with a drop in hemoglobin (Hgb) of ≥ 5 g/dL or an absolute drop in hematocrit of at least 15% (when Hgb not available) .

2. Minor

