Any clinically overt signs of hemorrhage (including imaging) that is associated with a fall in Hgb of 3 to < 5 g/dL (when a Hgb value was not available, a fall in the hematocrit of 9 % to <15% points) if no bleeding site was identifiable, or drop of ≥ 40 g/L in hemoglobin (or $\geq 12\%$ in hematocrit)

3. Medical Attention:

Any overt sign of hemorrhage that requires medical evaluation, medical treatment (including discontinuation of medications), or surgical treatment, and that does not meet criteria for a major or minor bleeding event, as defined above.

4. Minimal

Any overt bleeding event that does not meet the criteria above

Relationship of Bleeding to Death

1. Fatal Bleeding

Death in which a bleeding event directly led to death within 7 days. Examples of fatal bleeding events are an intracranial hemorrhage that led to herniation of the brain and death within 24 hours, and a massive gastrointestinal hemorrhage that results in shock, hemodynamic collapse, and death. If a bleeding event is considered fatal, then the cause of death must be either intracranial or non-intracranial bleeding.

2. Bleeding Contributed to Death

Death in which a bleeding event was part of a causal chain of medical events that ultimately led to death within 30 days of the bleed, but bleeding was not directly and/or immediately related to the subject's death. An example of bleeding contributing to death is a large retroperitoneal bleed that leads to surgical evacuation, development of a subsequent abscess in the area of bleeding that leads to sepsis, multiorgan failure, and death 10 days after the onset of bleeding. If bleeding has contributed to death (but the bleeding was not categorized as "fatal"), then the cause of death must be recorded as something other than intracranial / non-intracranial bleeding.

c. Bleeding in the Setting of Coronary Artery Bypass Graft Surgery (CABG)

Minor and minimal bleeding are not adjudicated in the setting of CABG.

As a drop in hemoglobin and transfusions are commonplace in routine CABG cases, one of the following criteria must be met to qualify for major bleeding in any of the preceding definitions:

1. Fatal bleeding (i.e., bleeding that directly results in death)
2. Perioperative intracranial bleeding
3. Reoperation following closure of the sternotomy incision for the purpose of controlling bleeding

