4. Transfusion of ≥ 5 units of packed red blood cells (PRBCs) or whole blood within a 48 hour period. Cell saver transfusion will not be counted in calculations of blood products
5. Chest tube output > 2 L within a 24 hour period

ACUITY

Major Bleeding is defined as

1. Intracranial bleeding
2. Intraocular bleeding
3. Access site hemorrhage requiring intervention
4. ≥ 5 cm diameter hematoma
5. Reduction in hemoglobin concentration of ≥ 4 g/dL without an overt source of bleeding
6. Reduction in hemoglobin concentration of ≥ 3 g/dL with an overt source of bleeding
7. Reoperation for bleeding
8. Use of any blood product transfusion

Minor bleeding

Clinically overt bleeding that did not meet criteria for major bleeding.

Smoking Status

Smoker: regular cigarette smoking in the prior 6 months

Nonsmoker: no regularly cigarettes smoking at any time (according to WHO also former smoker that quit smoking for at least 10 years).

Former smoker: those who had quit smoking at least 6 months before the index PCI.

Diabetes Mellitus

Active treatment with insulin or an oral hypoglycemic agent on admission. In patients diagnosed with diabetes who are on dietary therapy alone, documentation of an abnormal fasting blood glucose (>125 mg/dl), blood glucose >200mg/dl at any time, or abnormal glucose tolerance test based on the World Health Organization criteria is required.

Family History of Premature CAD

Myocardial infarction, angiographic documentation of CAD or sudden abrupt death without obvious cause, before the age of 55 in a first-degree blood male relative (parent, sibling, or children related by blood) or before the age of 65 in a first-degree blood female relative.

History of Hypercholesterolemia

Patients with any one of the following:

1. Prior total cholesterol > 200 mg/dl
2. Prior treatment with a lipid lowering agent

Arterial Hypertension

Arterial hypertension is considered to be present when a person's systolic blood pressure is 140 mmHg or greater, and/or their diastolic blood pressure is 90 mmHg or greater on 2 different occasions, or active treatment with antihypertensive drugs.

Multivessel Disease

Presence of angiographically significant lesions (>50% lumen narrowing) in ≥ 2 major epicardial coronary arteries.

Renal failure

A creatinine value of more than 133 $\mu\text{mol/l}$ or patients in dialysis.

Statistical Considerations

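### The TIMI Minor bleeding sentence is mis-constructed: read literally, known-site overt bleeds with a 3 to <4 g/dL fall leave the bleeding endpoint, and overt falls of 5 g/dL or more fit two classes

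*Combined protocol and SAP*

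**What the plan says.** The combined protocol and SAP chooses the scale under Major bleeding definitions: "For the bleeding secondary endpoint the TIMI (major and minor) criteria will be used". GUSTO and ACUITY classes are recorded for description only. The outcome is item 10 of the secondary endpoints: "Bleeding at 48 hr and 12 months".

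The TIMI classes are set out under Definitions:

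- **Major** is any intracranial bleed, or "Clinically overt signs of hemorrhage associated with a drop in hemoglobin (Hgb) of ≥ 5 g/dL". A haematocrit drop of at least 15% stands in when haemoglobin is missing.
- **Minor** opens with "Any clinically overt signs of hemorrhage (including imaging) that is associated with a fall in Hgb of 3 to < 5 g/dL", gives a bracketed haematocrit substitute of 9 to <15 points, and goes on "if no bleeding site was identifiable, or drop of ≥ 40 g/L in hemoglobin" (or at least 12% in haematocrit).
- **Medical Attention** and **Minimal** take the overt bleeds that fit neither class above.
- **CABG** has its own rules: Minor is not adjudicated there, and Major needs one of five separate criteria.

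**The concern.** The Minor sentence has two branches and one qualifying condition, and the condition appears to sit on the wrong branch. It asks for overt haemorrhage and, in the same branch, for an unidentifiable site. These two requirements pull against each other and shut out an ordinary puncture-site bleed. The second branch, where a larger fall might reasonably stand in for a missing source, carries no site condition and no ceiling.

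The protocol's own ACUITY list runs the other way: 3 g/dL is enough with an overt source, and 4 "g/dL without an overt source of bleeding" is required otherwise. That suggests a misplaced clause rather than a deliberate rule.

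At stake is which bleeds enter the endpoint. The affected bleeds have a known source. The protocol itself treats puncture-site bleeding as a concern, since Trial Conduct strongly recommends radial access to avoid it. Two adjudicators could classify the same bleed differently, and the text offers no tie-break.

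**Working it through.** The plan gives no figure to reproduce here. The check is to apply the rules as written.

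**Inputs** (Definitions, TIMI bleeding):

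- Major: intracranial, or overt with a fall ≥5 g/dL (haematocrit ≥15% if no haemoglobin).
- Minor, branch 1: overt, fall 3 to <5 g/dL (haematocrit 9 to <15 points if no haemoglobin), no site identifiable. The condition follows the bracket directly: "a fall in the hematocrit of 9 % to <15% points) if no bleeding site was identifiable".
- Minor, branch 2, after the comma: fall ≥40 g/L, or haematocrit ≥12%. Unit conversion: 40 g/L ÷ 10 = 4 g/dL.

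**Classification as punctuated** (non-intracranial, outside CABG, haematocrit drop below 12 points where the fall is under 4 g/dL):

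| Bleed | Fall, g/dL | Major | Minor |
|---|---|---|---|
| Overt, site known | 3 to <4 | no | no |
| Overt, site known | 4 to <5 | no | yes (branch 2) |
| Overt, site known | ≥5 | yes | yes (branch 2) |
| Overt, site not identified | 3 to <5 | no | yes |
| Overt, site not identified | ≥5 | yes | yes (branch 2) |
| Not overt, no site | ≥4 | no | only if branch 2 needs no overt signs |

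The first row is the gap: these bleeds fall to Medical Attention or Minimal, outside the endpoint. The gap is 4 − 3 = 1 g/dL of a band 5 − 3 = 2 g/dL wide. That is half of the haemoglobin range, not half of the events. The two ≥5 rows are the overlap.

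**Haematocrit used because haemoglobin is missing.** The pattern is the same. An overt known-site drop of 9 to <12 points is in neither class, 12 to <15 is Minor, and ≥15 is both.

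**Other ways to read the sentence:**

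- Overt signs govern both branches: the gap and the overlap both remain. Only the last row of the table changes.
- The no-site condition belongs to branch 2, against the word order: the gap closes. An overt fall ≥5 g/dL with no identified site is still both Major and Minor, because branch 2 has no ceiling.
- The no-site condition belongs to branch 2 and events meeting Major are excluded: no gap and no overlap.

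A ceiling of <5 g/dL on branch 2 would also remove the overlap. It would, however, leave a non-overt fall ≥5 g/dL with no site in neither class, since Major needs overt signs. Excluding events that meet Major avoids this.

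**The case against.** The strongest reply is that nobody would apply so garbled a sentence literally. The protocol says that its bleeding definitions are based on the cited trials' criteria, an independent committee adjudicates, and the classes form a descending list whose intended order is plain. Bleeds in the gap would also still be ACUITY major and so remain visible in the database. Part of this stands: the result is a risk of misclassification that depends on the reading, not a certain loss. But the committee works from this text, and ACUITY is descriptive, so neither repairs the endpoint.

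A reader might infer more than the documents support:

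- **That every known-site bleed in the gap is lost.** Intracranial bleeds are Major at any fall, a haematocrit drop of at least 12 points re-enters through branch 2, and CABG bleeds follow separate rules.
- **That double classification inflates the endpoint.** A patient counted once as major-or-minor is counted once either way. Only separate Major and Minor tallies are affected.
- **That this is the trial's main safety outcome.** The protocol lists it as secondary endpoint 10 of 11, and the safety criterion that it names for the DSMB is mortality.
- **That the FFR strategy adds PCI, so the gap hides harm in that arm.** Statistical Considerations expects 50% more procedures in the non-FFR arm. Its inputs for control patients (half FFR-positive with 70% revascularised, half negative with 50% revascularised) give 0.5 × 70% + 0.5 × 50% = 60% with non-IRA PCI. The FFR arm would have about 50%, if the same split is assumed there. The direction of any imbalance is unknown.

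**Conclusion.** The Minor sentence should be corrected. It states a threshold for a named secondary endpoint that would misclassify events if followed.

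The conclusion rests on reading the condition where the punctuation puts it. The overlap survives, for bleeds without an identified site, even if the condition is moved to the second branch without an exclusion of Major. The number of events cannot be computed, because the documents give no bleeding rates.

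The reach is limited. The primary endpoint has no bleeding component, and TIMI Major is unaffected. The net adverse clinical events composite is also unaffected, provided that its major bleeding means TIMI Major.

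**What to change.** Before bleeds are adjudicated, reword Minor so that:

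1. overt haemorrhage (including imaging) with a fall of 3 to <5 g/dL, or 9 to <15 haematocrit points if haemoglobin is unavailable, counts whether or not the site is known;
2. the no-site condition attaches to the branch of ≥4 g/dL (haematocrit ≥12 points), after confirmation against the cited TIMI criteria, because the internal support for it is only the analogy with ACUITY;
3. that branch says whether overt signs are needed: once item 1 is in place, it adds little on the haemoglobin criterion if they are, since Minor and Major already cover overt falls from 3 g/dL upward;
4. events meeting Major are excluded;
5. haemoglobin is in g/dL throughout.

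The cost is one sentence in the definitions and a matching line on the adjudication form. No new data are needed, because the ACUITY classes already require the haemoglobin fall and whether there is an overt source. Any bleeds already adjudicated should be reclassified under the corrected rule.
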